7.5 Preparation/Handling/Storage/Accountability

The investigational product should be stored in a secure area according to local regulations. It is the responsibility of the investigator to ensure that investigational product is only dispensed to study participants. The investigational product must be dispensed only from official study sites by authorized personnel according to local regulations.

The product storage manager should ensure that the study treatment is stored in accordance with the environmental conditions (temperature, light, and humidity) as determined by BMS. If concerns regarding the quality or appearance of the study treatment arise, the study treatment should not be dispensed and contact BMS immediately.

Investigational product documentation (whether supplied by BMS or not) must be maintained that includes all processes required to ensure drug is accurately administered. This includes documentation of drug storage, administration and, as applicable, storage temperatures, reconstitution, and use of required processes (eg, required diluents, administration sets).

For study drugs not provided by BMS and obtained commercially by the site, storage should be in accordance with the product label.

Further guidance and information for final disposition of unused study treatment are provided in [Appendix 2](#).

7.5.1 *Retained Samples for Bioavailability / Bioequivalence*

Not applicable.

7.6 *Treatment Compliance*

Study treatment compliance will be periodically monitored by drug accountability, and review of dosing diary cards. Drug accountability should be reviewed by the site study staff at each visit to confirm treatment compliance. Sites should discuss discrepancies with the participant at each on-treatment study visit.

7.7 *Concomitant Therapy*

7.7.1 *Prohibited and/or Restricted Treatments*

The following medications are prohibited during the study (unless utilized to treat a drug related adverse event):

- Immunosuppressive agents
- Immunosuppressive doses of systemic corticosteroids (except as stated in [Section 7.7.3](#))
- Any concurrent anti-neoplastic therapy (ie, chemotherapy, hormonal therapy, immunotherapy, radiation therapy, or standard or investigational agents for treatment of CRC)
- Any botanical preparation (eg herbal supplements or traditional Chinese medicines) intended to treat the disease under study or provide supportive care. Use of marijuana and its derivatives for treatment of symptoms related to cancer or cancer treatment are permitted if obtained by medical prescription or if its use (even without a medical prescription) has been legalized locally.
- Any live/attenuated vaccine (eg, varicella, zoster, yellow fever, rotavirus, oral polio and measles, mumps, rubella [MMR]) within 100 days post last dose of nivolumab without or with ipilimumab.
- Non-live Coronavirus Disease 2019 (COVID-19) vaccination is considered a simple concomitant medication within the study. However, the safety and efficacy of non-live vaccines (including non-live COVID-19 vaccines) in participants receiving nivolumab, ipilimumab, or trametinib are unknown.

The potential for overlapping toxicities with radiotherapy and nivolumab with or without ipilimumab in combination with trametinib is not known currently. Therefore, radiotherapy is not

permitted while receiving study treatment. If radiotherapy is required, participants should discontinue study treatment. Palliative radiotherapy for participants in the SOC arm receiving regorafenib may be administered per local product label and institutional guidelines.

- Refer to local product labels/institution guidelines for additional prohibited and/or restricted treatments for participants receiving regorafenib.

7.7.2 *Other Restrictions and Precautions*

Participants with a condition requiring systemic treatment with either corticosteroids (> 10 mg daily prednisone equivalent) or other immunosuppressive medications within 14 days of treatment assignment/randomization are excluded. Inhaled or topical steroids, and adrenal replacement steroid doses > 10 mg daily prednisone equivalent, are permitted in the absence of active autoimmune disease.

Any prescription or herbal product which is not prescribed by the investigator or licensed physician for treatment of a specific clinical condition is prohibited.

- Refer to local product labels/institution guidelines for additional restrictions and precautions for participants receiving regorafenib.

7.7.2.1 *Imaging Restriction and Precautions*

It is the local imaging facility's responsibility to determine, based on participant attributes (eg. allergy history, diabetic history and renal status), the appropriate imaging modality and contrast regimen for each participant. Imaging contraindications and contrast risks should be considered in this assessment. Participants with renal insufficiency should be assessed as to whether or not they should receive contrast and if so, what type and dose of contrast is appropriate. Should a participant have a contraindication for CT IV contrast, a non-contrast CT of the chest and a contrast enhanced MRI of the abdomen and pelvis may be obtained.

Specific to MRI, participants with severe renal insufficiency (ie, estimated glomerular filtration rate (eGFR) < 30 mL/min/1.73 m²) are at increased risk of nephrogenic systemic fibrosis. MRI contrast should not be given to this participant population. In addition, participants are excluded from MRI if they have tattoos, metallic implants, pacemakers, etc. The ultimate decision to perform MRI in an individual participant in this study rests with the site radiologist, the investigator and the standard set by the local Ethics Committee.

7.7.3 *Permitted Therapies*

Participants are permitted the use of topical, ocular, intra-articular, intranasal, and inhalational corticosteroids (with minimal systemic absorption). Adrenal replacement steroid doses > 10 mg daily prednisone are permitted. A brief (less than 3 weeks) course of corticosteroids for prophylaxis (eg, contrast dye allergy) or for treatment of non-autoimmune conditions (eg, delayed-type hypersensitivity reaction caused by a contact allergen) is permitted. Regular concomitant use

of bisphosphonates and RANK-L inhibitors for prevention or reduction of skeletal-related events in participants with bone metastases is allowed if initiated prior to first dose of study treatment.

Hormone replacement therapy: Participants may continue to receive hormonal replacement therapy if initiated prior to treatment assignment/randomization.

Supportive Care: For participants receiving regorafenib, follow local product label, institutional guidelines, or relevant regional guidelines (eg, ASCO or ESMO) to manage expected toxicities. Supportive care includes, but is not limited to, hematologic support and management of diarrhea, nausea/vomiting, skin toxicities, as well as prophylactic or therapeutic administration of appropriate therapies.

7.8 Treatment After the End of the Study

At the conclusion of the study, participants who continue to demonstrate clinical benefit will be eligible to receive BMS supplied study treatment **for the maximum treatment duration specified in protocol Section 5.4.1**. Study treatment will be provided via an extension of the study, a rollover study requiring approval by responsible health authority and ethics committee or through another mechanism at the discretion of BMS.

BMS reserves the right to terminate access to BMS supplied study treatment if any of the following occur: a) the study is terminated due to safety concerns; b) the development of study drugs is terminated for other reasons, including but not limited to lack of efficacy and/or not meeting the study objectives; c) the participant can obtain medication from a government sponsored or private health program. In all cases BMS will follow local regulations.

8 DISCONTINUATION CRITERIA

8.1 Discontinuation from Study Treatment

Participants MUST discontinue investigational product (and non-investigational product at the discretion of the investigator) for any of the following reasons:

- Participant's request to stop study treatment. Participants who request to discontinue study treatment will remain in the study and must continue to be followed for protocol specified follow-up procedures. The only exception to this is when a participant specifically withdraws consent for any further contact with him/her or persons previously authorized by participant to provide this information
- Any clinical adverse event (AE), laboratory abnormality or intercurrent illness which, in the opinion of the investigator, indicates that continued participation in the study is not in the best interest of the participant. Adverse events should be graded and managed according to NCI CTCAE (version 4.0) guidelines.
- Termination of the study by Bristol-Myers Squibb (BMS)
- Loss of ability to freely provide consent through imprisonment or involuntarily incarceration for treatment of either a psychiatric or physical (eg, infectious disease) illness. (Note: Under specific circumstances, and only in countries where local regulations permit, a participant who has been imprisoned may be permitted to continue as a participant. Strict conditions apply and BMS approval is required.)

- Documented radiographic disease progression per RECIST v1.1.
 - Note: For 2L and 3L+ mCRC participants in Cohorts 4 and 6, treatment beyond progression is permitted. See [Section 8.1.5](#).
- Criteria listed in [Section 8.1.1](#) thru [8.1.4](#).
- Requiring treatment as listed in [Section 7.7](#).

Any criteria leading to the discontinuation of nivolumab, ipilimumab, or trametinib as part of the triplet investigative regimen in Parts 1B and 2 will require discontinuation of the entire regimen.

Discontinuation of the study treatment for abnormal liver tests should be considered by the investigator when a participant meets one of the conditions outlined in the protocol ([Section 8.1](#), [Appendix 5](#), and [Appendix 6](#)) or if the investigator believes that it is in best interest of the participant.

Refer to the Schedule of Activities for data to be collected at the time of treatment discontinuation and follow-up and for any further evaluations that can be completed.

In the case of pregnancy, the investigator must immediately, within 24 hours of awareness of the pregnancy, notify the BMS Medical Monitor/designee of this event. In most cases, the study treatment will be permanently discontinued in an appropriate manner (eg, dose tapering if necessary for participant safety). Refer to [Section 9.2.5](#) Pregnancy.

All participants who discontinue study treatment should comply with protocol specified follow-up procedures as outlined in [Section 2](#). The only exception to this requirement is when a participant withdraws consent for all study procedures including post-treatment study follow-up or loses the ability to consent freely (ie, is imprisoned or involuntarily incarcerated for the treatment of either a psychiatric or physical illness).

If study treatment is discontinued prior to the participant's completion of the study, the reason for the discontinuation must be documented in the participant's medical records and entered on the appropriate case report form (CRF) page.

The assessment for discontinuation of nivolumab should be made separately from the assessment made for discontinuation of ipilimumab. Although there is overlap among the discontinuation criteria, if discontinuation criteria are met for ipilimumab but not for nivolumab, treatment with nivolumab may continue if ipilimumab is discontinued.

If a participant in any of the nivolumab/ipilimumab combination arms meets criteria for discontinuation and investigator is unable to determine whether the event is related to both or one study drug, the participant should discontinue both nivolumab and ipilimumab and be taken off the treatment phase of the study.

Participants are permitted to continue with nivolumab in combination with trametinib if deemed medically appropriate by the treating physician to manage toxicity, and in consultation with Medical Monitor/designee. Continuation with ipilimumab in combination with trametinib is not

permitted. For participants in Part 1A or Part 1, changes in study treatment are not permitted during the DLT observation period. See [Section 7.1.2](#) trametinib dosing for further detail.

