7.4.1 Nivolumab/Ipilimumab Dose Delay

Nivolumab or ipilimumab administration should be delayed for the following:

- Grade 2 non-skin, drug-related adverse event, with the exception of fatigue
- Grade 2 drug-related creatinine, AST, ALT, and/or Total Bilirubin abnormalities
- Grade 3 skin, drug-related adverse event

- Grade 3 drug-related laboratory abnormality, with the following exceptions:
 - Grade 3 lymphopenia or asymptomatic amylase or lipase does not require dose delay
 - Grade ≥ 3 AST, ALT, Total Bilirubin will require dose discontinuation (see [Section 8.1.1](#))
- Any adverse event, laboratory abnormality, or intercurrent illness which, in the judgment of the investigator, warrants delaying the dose of study medication.

Participants who require delay of nivolumab/ipilimumab should be re-evaluated weekly or more frequently if clinically indicated and resume nivolumab/ipilimumab dosing when re-treatment criteria are met.

Further detail on immune related adverse event management algorithm is described in [Appendix 5](#) for the following categories:

- GI Adverse Event
- Renal Adverse Event
- Pulmonary Adverse Event
- Hepatic Adverse Event
- Endocrinopathy Management
- Skin Adverse Event
- Neurological Adverse Event
- Myocarditis Adverse Event

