7.4.2 Criteria to Resume Treatment with Nivolumab or Ipilimumab

Participants may resume treatment with study drug when the drug-related AE(s) resolve to Grade ≤ 1 or baseline value, with the following exceptions:

- Participants may resume treatment in the presence of Grade 2 fatigue;
- Participants who have not experienced a Grade 3 drug-related skin AE may resume treatment in the presence of Grade 2 skin toxicity;
- For participants with Grade 2 AST, ALT and/or Total Bilirubin Abnormalities, dosing may resume when laboratory values return to baseline and management with corticosteroids, if needed, is complete;
- Drug-related pulmonary toxicity, diarrhea or colitis must have resolved to baseline before treatment is resumed. Participants with persistent Grade 1 pneumonitis after completion of a steroid taper over at least 1 month may be eligible for retreatment if discussed with and approved by BMS Medical Monitor/designee;
- Participants with drug-related endocrinopathies adequately controlled with only physiologic hormone replacement may resume treatment after consultation with the BMS Medical Monitor/designee. Adrenal insufficiency requires discontinuation regardless of control with hormone replacement.

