> 3 times ULN (Grade 2 or higher) with concurrent bilirubin > 2 times ULN	Any occurrence	Discontinue treatment with regorafenib permanently. Monitor liver function weekly until resolution or return to baseline. Exception: Patients with Gilbert's syndrome who develop elevated transaminases should be managed as per the above outlined recommendations for the respective observed elevation of ALT and/or AST.

Source: Modified from Table 2 of regorafenib SmPC

Table 7.4.6-2: Recommended Dose Modifications and Measures for HFSR

Skin Toxicity Grade	Occurrence	Recommended Dose Modification and Measures
Grade 1	Any	Maintain dose level and immediately institute supportive measures for symptomatic relief.
Grade 2	1st occurrence	Decrease dose by 40 mg (1 tablet) and immediately institute supportive measures. If no improvement occurs despite dose reduction, interrupt therapy for a minimum of 7 days, until toxicity resolves to Grade 0-1. A dose re-escalation is permitted at the discretion of the physician.
	No improvement within 7 days or 2nd occurrence	Interrupt therapy until toxicity resolves to Grade 0-1. When re-starting treatment, decrease dose by 40 mg (1 tablet). A dose re-escalation is permitted at the discretion of the physician.
	3rd occurrence	Interrupt therapy until toxicity resolves to Grade 0-1. When re-starting treatment, decrease dose by 40 mg (1 tablet). A dose re-escalation is permitted at the discretion of the physician.
	4th occurrence	Discontinue treatment with regorafenib permanently.
Grade 3	1st occurrence	Institute supportive measures immediately. Interrupt therapy for a minimum of 7 days until toxicity resolves to Grade 0-1. When re-starting treatment, decrease dose by 40 mg (1 tablet). A dose re-escalation is permitted at the discretion of the physician.
	2nd occurrence	Institute supportive measures immediately. Interrupt therapy for a minimum of 7 days until toxicity resolves to Grade 0-1. When re-starting treatment, decrease dose by 40 mg (1 tablet).
	3rd occurrence	Discontinue treatment with regorafenib permanently.

Source: Modified from Table 1 of regorafenib SmPC

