8.1.2 Nivolumab and Ipilimumab Dose Discontinuation

For participants who receive nivolumab in combination with ipilimumab and trametinib, study treatment should be permanently discontinued for the following:

- Any Grade 2 drug-related uveitis, eye pain or blurred vision that does not respond to topical therapy and does not improve to Grade 1 severity within the re-treatment period OR requires systemic treatment
- Any Grade 3 non-skin, drug-related adverse event lasting > 7 days, or recurs, with the following exceptions for laboratory abnormalities, diarrhea, colitis, neurologic toxicity, drug-related uveitis, pneumonitis, bronchospasm, hypersensitivity reactions, infusion reactions, and endocrinopathies:
 - Grade 3 drug-related diarrhea, colitis, neurologic toxicity, uveitis, pneumonitis, bronchospasm, myocarditis, hypersensitivity reaction, or infusion reaction of any duration requires discontinuation
 - Grade 3 drug-related endocrinopathies, adequately controlled with only physiologic hormone replacement do not require discontinuation. Adrenal insufficiency requires discontinuation regardless of control with hormone replacement.
 - Grade 3 drug-related laboratory abnormalities do not require treatment discontinuation except:
 - ◆ Grade 3 drug-related thrombocytopenia > 7 days or associated with bleeding requires discontinuation
 - ◆ Any drug-related liver function test (LFT) abnormality that meets the following criteria require discontinuation:
 - Grade \geq 3 drug-related AST, ALT or Total Bilirubin requires discontinuation*

- Concurrent AST or ALT $> 3 \times$ ULN and total bilirubin $> 2 \times$ ULN

* In most cases of Grade 3 AST or ALT elevation, study treatment(s) will be permanently discontinued. If the investigator determines a possible favorable benefit/risk ratio that warrants continuation of study treatment(s), a discussion between the investigator and the BMS Medical Monitor/designee must occur.

- Any Grade 4 drug-related adverse event or laboratory abnormality (including but not limited to creatinine, AST, ALT, or Total Bilirubin), except for the following events which do not require discontinuation:
 - Grade 4 neutropenia ≤ 7 days
 - Grade 4 lymphopenia or leukopenia or asymptomatic amylase or lipase
 - Isolated Grade 4 electrolyte imbalances/abnormalities that are not associated with clinical sequelae and are corrected with supplementation/appropriate management within 72 hours of their onset

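### Section 8.1 both requires stopping for abnormal liver tests and leaves it to the investigator, and a concurrent Grade 2 transaminase and bilirubin rise meets both a stopping rule and a delay-and-resume rule

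*Combined protocol and SAP*

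**What the plan says.** All references are to the protocol.

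- **Section 8.1, list.** It begins "Participants MUST discontinue investigational product (and non-investigational product at the discretion of the investigator) for any of the following reasons", and one of the listed reasons is any criterion in Sections 8.1.1 to 8.1.4.
- **Section 8.1, later paragraph.** "Discontinuation of the study treatment for abnormal liver tests should be considered by the investigator when a participant meets one of the conditions". The conditions are those of Section 8.1, Appendix 5 and Appendix 6, or the investigator's view of the participant's best interest.
- **Section 8.1.2 (triplet).** "Any drug-related liver function test (LFT) abnormality that meets the following criteria require discontinuation". There are two criteria: Grade 3 or higher AST, ALT or total bilirubin; and AST or ALT above 3 × ULN together with total bilirubin above 2 × ULN. A footnote to the first allows continuation after a Medical Monitor discussion, for Grade 3 AST or ALT only. The concurrent criterion has no footnote. Section 8.1.1, headed as Part 1 only, has the same pair.
- **Section 7.4.1.** Dosing is delayed for "Grade 2 drug-related creatinine, AST, ALT, and/or Total Bilirubin abnormalities". Grade 3 or higher AST, ALT or bilirubin is sent to discontinuation, with a pointer to Section 8.1.1.
- **Section 7.4.2.** "For participants with Grade 2 AST, ALT and/or Total Bilirubin Abnormalities, dosing may resume when laboratory values return to baseline", once any corticosteroid course is complete.

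In Parts 1B and 2, a criterion that stops one component of the triplet stops the whole regimen (Sections 8.1 and 8.1.2).

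**The concern.** Two sites holding the same laboratory report could act differently and each cite the protocol. One could stop the triplet permanently under the Section 8.1 list and 8.1.2. Another could treat stopping as a matter of judgement under the later paragraph of 8.1. In one band of values, a third could hold the dose and restart at baseline under 7.4.1 and 7.4.2.

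The pattern is not trivial by the protocol's own standard. For participants with normal baseline values, Section 9.2.7 treats AST/ALT above 3 × ULN with bilirubin above 2 × ULN, without cholestasis or another apparent cause, as potential drug-induced liver injury to be reported as an SAE.

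For the analysis, adverse events leading to discontinuation are a planned safety summary (Section 10.3.2). Those counts, and exposure to the triplet in Cohorts 4 and 6, would partly reflect which section a site read. The effect on the primary endpoint is indirect, because the response window in Section 10.3.1 closes at progression or subsequent therapy, not when treatment stops.

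**Working it through.** The plan gives no figure to reproduce. The check sets the rules side by side by region of AST/ALT and bilirubin.

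**Grade boundaries.** Table 7.4.6-1 prints AST/ALT up to 5 × ULN as at most Grade 2, above 5 and up to 20 × ULN as Grade 3, and above 20 × ULN as Grade 4. It labels AST/ALT above 3 × ULN as Grade 2 or higher. So AST/ALT above 3 and up to 5 × ULN is exactly Grade 2. No bilirubin grade boundary is printed. Let U be the upper Grade 2 limit for bilirubin, in multiples of ULN.

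**Rules applied to a drug-related abnormality in a triplet participant:**

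| Pattern | 8.1 list | 8.1 later paragraph | 8.1.2 | 7.4.1 / 7.4.2 |
|---|---|---|---|---|
| A. AST/ALT > 3 to ≤ 5 × ULN, bilirubin > 2 to ≤ U × ULN | must stop | consider | stop, no exception | delay; may resume at baseline |
| B. AST/ALT Grade 3, bilirubin ≤ 2 × ULN | must stop | consider | stop, with discussed exception | discontinue |
| C. AST/ALT Grade 3, bilirubin > 2 to ≤ U × ULN | must stop | consider | stop; the concurrent criterion has no exception | discontinue |
| D. AST/ALT Grade 4, or bilirubin Grade 3 or higher | must stop | consider | stop; footnote does not reach it | discontinue |
| E. Grade 2, both concurrent thresholds not met | not triggered | not triggered through 8.1 | not triggered | delay; may resume at baseline |

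**First conflict (rows A to D).** The second and third columns disagree in every row where 8.1.2 is triggered. The softer paragraph names Section 8.1 as a source of its conditions, so it cannot be confined to milder abnormalities outside the list. This needs no assumption about grades.

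**Second conflict (row A only).** Example: AST 4 × ULN with bilirubin 2.5 × ULN.

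- 4 > 3 and 2.5 > 2, so the concurrent criterion of 8.1.2 is met.
- 3 < 4 ≤ 5, so AST is Grade 2 and the delay rule of 7.4.1 is met.
- If U ≥ 2.5, bilirubin is below Grade 3, nothing in 7.4.1 redirects the site to discontinuation, and 7.4.2 allows resumption.

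With bilirubin at 1.8 × ULN instead, 1.8 ≤ 2 and the case moves to row E, where nothing conflicts.

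**Dependence on U.** Row A spans bilirubin above 2 and up to U × ULN. If U ≤ 2 it is empty. If 2 < U < 2.5 it exists, but the example falls outside it. If U ≥ 2.5 the example is inside. The text implies U > 2: if every bilirubin above 2 × ULN were already Grade 3, the Grade 3 bilirubin criterion alone would compel stopping and the concurrent criterion would add nothing.

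**Cross-reference.** For Grade 3 or higher, 7.4.1 points to 8.1.1, which covers Part 1 only. A triplet site is not led to 8.1.2, where the concurrent criterion for its participants sits.

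**The case against.** The best reply is that all the instructions can be obeyed at once. Section 7.4.2 only permits resumption; it does not exempt anyone from Section 8. A site that delays the dose and then applies the mandatory list breaches nothing. That has force: it would overstate the case to say that the protocol offers three actions of equal standing. But the reply relies on the list prevailing, and the later paragraph of 8.1 weakens the list for exactly these tests. Section 7.4.2 does restate an overriding stop for adrenal insufficiency, so its silence here gives the site no signal.

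The concurrent criterion also sits beneath a bullet about Grade 3 laboratory abnormalities, which might suggest that it starts at Grade 3. In 8.1.2, however, its lead-in covers any drug-related liver abnormality and its thresholds carry no grade.

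The instructions to follow the most conservative guideline (Sections 3.3 and 7.4, Appendices 5 and 6) will help in many cases, since Section 3.3 expects overlapping liver toxicity. They address combination-related events and Appendix 5 against Appendix 6. For events attributed to nivolumab/ipilimumab only, Section 7.4 sends the site to 7.4.1 and Appendix 5. SAE reporting and the Section 9 duty to discuss immediate safety concerns with the sponsor reduce the practical risk, but do not say which rule governs.

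Three stronger readings are tempting:

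- **Every concurrent rise is affected.** It is not: both thresholds must be crossed with both values below Grade 3.
- **The concurrent criterion is idle once AST/ALT reaches Grade 3.** It is not: row C shows that it removes the footnote's discretion.
- **Regorafenib has the same stop-or-resume split.** It does not. For this pattern Table 7.4.6-1 says "Discontinue treatment with regorafenib permanently. Monitor liver function weekly until resolution or return to baseline", with an exception for Gilbert's syndrome, and Section 8.1.4 agrees and falls under the mandatory list. Section 7.4.6 is a recommendation, and only the loose sentence in 8.1 touches that arm.

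**Conclusion.** The point holds in two parts. First, Section 8.1 contradicts itself and Sections 8.1.1/8.1.2 on whether meeting a liver criterion compels stopping; this rests on the printed words alone. Second, a drug-related rise with AST/ALT above 3 and up to 5 × ULN and bilirubin above 2 × ULN but still Grade 2 falls under both a stopping rule and a delay-and-resume rule. The second part assumes that the Grade 2 limit for bilirubin exceeds 2 × ULN, as the text implies but does not print. At Grade 3 or higher the delay section and 8.1.2 agree, apart from the misdirected cross-reference.

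The documents give no frequency for this pattern, so the number of participants affected cannot be estimated. Enrollment closed on 30-Nov-2022, which limits future exposure, but Section 5.1 keeps treatment running to about 9 months after the last participant's first treatment, and possibly longer.

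One limit remains: the Appendix 5 hepatic algorithm and Appendix 6 liver guidance are not shown, and either might contain wording that bears on this. The inconsistency is worth correcting because it is safety-relevant and cheap to remove. Nothing here says which action is clinically right.

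**What to change.** Reconcile four places so that each liver-test pattern leads to one instruction: the mandatory list in 8.1, the later liver paragraph in 8.1, the liver criteria in 8.1.1/8.1.2, and the delay and resumption rules in 7.4.1/7.4.2. State in 7.4.1 and 7.4.2 how they apply when the concurrent AST/ALT-and-bilirubin criterion is met. Correct the 7.4.1 cross-reference so that triplet participants are directed to the section that covers them. Check the result against the Appendix 5 hepatic algorithm and the Appendix 6 liver guidance. The sponsor's clinical team decides which action applies to each pattern.

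The cost is a few words in Sections 7.4.1, 7.4.2 and 8.1 to 8.1.2, by administrative letter or with the next amendment. No new data or procedures are needed.
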